	
randomized/enrolled subjects will be summarized. The number and percentage of subjects included in different analysis data sets will be calculated for each dose group.
 
Statistical Analysis of C-QTC Study:
 
Exploratory statistical analysis will be performed on C-QTc based on PK and QT interval changes. Descriptive analysis will be performed for QT/QTc intervals and changes from baseline at each time point, and line charts will be used to depict the changes at each time point and between groups. Baseline correction (<math>\Delta</math>QTc) and placebo correction (<math>\Delta\Delta</math>QTc) will be applied to the obtained QT/QTc intervals, with <math>\Delta</math>QTc as the dependent variable to measure the degree of drug effect on QT/QTc. The changes in drug concentration and QT/QTc intervals will be considered for model-based exploratory analysis.
 
Tolerability and Safety Evaluation:
 
Statistical analysis will be performed using SAS (v9.4 or above).
 
Adverse events (AEs) will be coded as per the Medical Dictionary for Regulatory Activities (MedDRA). The AEs observed during the trial will be described by system organ class (SOC) and preferred term (PT) for each dose group. Descriptive statistics of clinical laboratory tests, 12-lead ECGs, C-QTc study, vital signs, and physical examination results will be performed for each dose group. Clinically significant changes in clinical laboratory findings from baseline will be presented in the shift table.
 
Evaluation of the C-QTc study: The threshold of concern is a <math>\Delta\Delta</math>QTc interval prolongation exceeding 5 ms. Based on the C-QTc study results, it can be confirmed whether the conditions for conducting a TQT study are met. According to the C-QTc model, if the upper limit of two-sided 90% CI for <math>\Delta\Delta</math>QTcF corresponding to the highest clinical exposure is <math>\leq</math> 10 ms, it can be considered that the mean QT/QTc effect of the drug is not more than 5 ms, and the C-QTc study result is negative. However, if the upper limit of two-sided 90% CI for <math>\Delta\Delta</math>QTcF corresponding to low clinical exposure is <math>></math> 10 ms by model calculation, the C-QTc study result will be positive. When the upper limit of two-sided 90% CI for <math>\Delta\Delta</math>QTcF corresponding to low clinical exposure is <math>\leq</math> 10 ms and the upper limit of two-sided 90% CI for <math>\Delta\Delta</math>QTcF corresponding to the highest clinical exposure is <math>></math> 10 ms, the dose range for negative <math>\Delta\Delta</math>QTcF (<math>\leq</math> 10 ms) can be obtained with the model.
 
Pharmacokinetic Analysis:
 
Plasma concentrations will be summarized by dose group and scheduled sampling time point, including the number of subjects, the number of subjects below the quantification limit (BQL), arithmetic mean, standard deviation, coefficient of variation, median, minimum, maximum, geometric mean, and geometric coefficient of variation. Individual and mean plasma concentration-time (C-T) curves will be plotted separately.
 
Based on the non-compartmental model, Phoenix WinNonlin software (Certara USA Inc, version 8.2 or above) will be used to calculate PK parameters (main PK parameters include <math>T_{max}</math>, <math>C_{max}</math>, and AUC). PK parameters will be summarized by dose group, including the number of subjects, arithmetic mean, standard deviation, median, minimum, and

--	--

maximum. For PK parameters, other than  $T_{max}$ , the coefficient of variation (CV, based on the arithmetic mean), geometric mean, and geometric CV will also be derived.

Descriptive statistics of main PK parameters post-dose will be performed using the Statistical Analysis Software (SAS, v9.4 or above) for each dose group, including a comparison of  $T_{max}$  between groups using a non-parametric test. An exploratory analysis of PK parameters (AUC and  $C_{max}$ ) versus dose will be conducted for potential dose proportionality. The relationship of log-transformed PK parameters against the log-transformed dose (fixed effect) will be fitted using the Power model to calculate the slope ( $\beta$ ) and its 90% confidence interval (CI) on the log scale.

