	
Overall Design
 
This study is a single-center, randomized, double-blind, multiple ascending doses (MAD), placebo-controlled phase Ib/IIa clinical trial of BGT-002 Tablets in subjects with NASH to evaluate the safety, tolerability, pharmacokinetics (PK) and early pharmacodynamics (PD) of BGT-002 Tablets.
 
The number of subjects: A total of 48–60 subjects are planned to be enrolled in this study.
 
Study Flow
 
Study Schedule:
 
This study includes the screening period (D-56–D-1), run-in period (D-56–28–D-1), treatment and observation period (D1–D29), and follow-up period (D30–D56). There will be a total of 8 return visits in the 50 mg and 75 mg groups: Visit 1-D-56–D-1 in the Screening Period, Visit 2-D-56–28–D-1 in the Run-in Period, Visit 3-D-1 at the End of Run-in Period, Visits 4–8-D15, D22, D26, and D27 in the Treatment and Efficacy Observation Period. The Follow-up Period will be D56 ± 5 days and there will be 2 hospitalization periods: 9 days in D-1–D8 and 3 days in D27–D29. In addition to the above visits, return visits will be required for patients in the 100 mg, 150 mg, and 200 mg (alternative) groups on D31, D35, D38, and D41. During the study, if necessary, additional visits may be added according to the individual conditions of the subjects.
 
After signing the informed consent form, subjects will enter the screening period (D-56–D-1) for preliminary eligibility evaluation. Subjects who pass the preliminary screening will enter a 4 to 8-week run-in period (D-56–28–D-1), during which subjects will be required to maintain their previous living habits and diet structure. If subjects have received one body weight measurement and MRI-PDFF examination and have obtained the results before screening, they will be subject to another body weight measurement, MRI-PDFF examination, and other screening tests at an interval of 4–8 weeks from the first time. Subjects who meet the enrollment criteria will be admitted to the ward on D-1, receive randomization in this trial, and enter the treatment and observation period (D1–D29). During the treatment and observation period (D1–D28), subjects will be given BGT-002 tablets or a placebo according to the randomization number every morning under fasting conditions. After completing the corresponding visit, they can enter the follow-up period (D30–D56).
 
All adverse events should be observed and recorded from post-administration to the end

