#### ➤ **Dose Ascending Principle:**

- 1) In this trial, it is planned to start with 50 mg as the lowest dose and 200 mg as an alternative dose. A total of 4 to 5 dose groups will be selected from 50 mg, 75 mg, 100 mg, 150 mg, and 200 mg (alternative) groups, and the trial will be gradually carried out according to the above set doses.
- 2) After the investigator and sponsor determine that 50% of subjects in each dose group have good results for 14-day safety evaluations, the trial can proceed to the next dose group. If necessary, subsequent trial protocols may be appropriately adjusted based on previous safety and PK analysis results (such as increasing or decreasing administration observation time or dose).
- 3) If the criteria for termination of dose ascending are met during dose ascending, even if the predetermined maximum dose has not been reached, the dose ascending should be terminated.

	
4) After the maximum estimated dose is reached by dose ascending, the investigator and the sponsor will discuss and analyze the existing safety and PK data before deciding whether to continue the next dose exploration. Any continuation will be subject to the approval of the Ethics Committee.
 
➤ Stopping Criteria for Dose Ascending:
 
Within 14 days after the first dose, if any of the following criteria are met, the investigator and the sponsor will discuss and analyze the reasons and judge the impact on subsequent trials to decide whether to terminate dose ascending:
 
 
1)In the same dose group, more than 1/2 of subjects experience Grade 2 and above AEs related to the study drug; or more than 1/3 of subjects experience Grade 3 and above AEs related to the study drug;
 
2)The trial should be suspended if 1 case of serious adverse event (SAE) related to the study drug occurs during the trial;
 
3)Based on the available PK data, the investigator agrees with the sponsor that there is no need to continue the trial.
 

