Dosing Regimen	
In this trial, the drug will be orally administered under fasting conditions, once in the morning with warm water for 4 consecutive weeks. Subjects will be required to fast for at least 10 h pre-dose on D1 and D28 and 4 h post-dose on the days of intensive blood sampling (D1 and D28) (intolerant subjects can take food 30 min post-dose). For the rest of the time (D2–D27), subjects should try to fast for 30 min post-dose. Except for water deprivation 1 h pre-dose and 2 h post-dose on the days of intensive blood sampling (D1 and D28), subjects can have free access to water in the rest time (D2–D27). Subjects will be required to remain sitting and out-of-bed activities will be limited within 2 h post-dose on D1 and D28 (transient lying position can be kept during ECG examination). Normal indoor activities will be allowed for the rest of the time, while excessive activity or prolonged bed rest should be avoided. Daily dosing shall be conducted at the same time as far as possible.
 
Treatment and Observation Period (4 weeks after treatment)
 
Study drug: Administered once daily in the morning under fasting conditions for 4 consecutive weeks.
 
Placebo: Administered once daily in the morning under fasting conditions for 4 consecutive weeks.

Examination Items and Time in Screening Period	
The screening physical examination will be performed on D-56–D-1 of administration, and the screening examination items include the following: Measurement of height and weight; vital signs; physical examination; HbA1c (only in diabetics and when needed); hematology; blood biochemistry; chest X-ray (PA view); urinalysis; four coagulation tests; thyroid function; ANA test; blood pregnancy test (for females only); abdominal B-scan ultrasonography (liver, gallbladder, pancreas, spleen and both kidneys); Fibroscan; MRI-PDFF; infectious disease screening; and 12-lead electrocardiogram (ECG)

	
examination.
 
Results of infectious disease screening, chest X-ray, and abdominal B-scan ultrasonography obtained within 1 month before screening will be considered valid. MRI-PDFF results obtained within 8 weeks before screening will be regarded as screening examination results and no additional examination will be required.

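### Criterion 1 for stopping dose ascending counts related adverse events for only the first 14 of 28 dosing days, so non-serious events on D15–D28 have no predefined group-level trigger in the synopsis or SAP

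*Protocol*

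**What the plan says.** All of this is in the Protocol Synopsis unless another source is named.

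- **Stopping Criteria for Dose Ascending.** The lead-in to all three criteria reads "Within 14 days after the first dose, if any of the following criteria are met". The investigator and sponsor then discuss the cause and decide whether to end dose ascending. Criterion 1 is the proportion rule (over 1/2 with related Grade 2+, or over 1/3 with related Grade 3+) and gives no window of its own. Criterion 2 reads "The trial should be suspended if 1 case of serious adverse event (SAE) related to the study drug occurs during the trial". Criterion 3 concerns PK.
- **Dose Ascending Principle.** Under principle 2, the next group may open once "50% of subjects in each dose group have good results for 14-day safety evaluations". Principle 3 says that ascending should end if the stopping criteria are met. Principle 4 requires discussion of "the existing safety and PK data before deciding whether to continue the next dose exploration" after the maximum planned dose.
- **Dosing Regimen.** The drug is taken "once in the morning with warm water for 4 consecutive weeks".
- **Study Flow.** "All adverse events should be observed and recorded from post-administration to the end" of the trial. Follow-up runs to D56.
- **SAP 6.5.1.** Adverse events are summarised descriptively. No stopping rule is added.

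**The concern.** Safety and tolerability is the primary objective, and each group is dosed for four weeks. The sponsor has judged that related events in more than half (Grade 2+) or more than a third (Grade 3+) of a group call for a formal discussion. If the same burden first appeared in week 3 or 4 without being serious, criterion 1 as worded would not be met.

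The second half of dosing is also the less-known half. In the synopsis table of earlier trials, repeat dosing went no further than 75 mg/day for 14 days. What is at stake is whether a late tolerability problem at 150 mg would prompt the prescribed discussion while subjects are being exposed to 200 mg.

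**Working it through.** **Step 1: what covers D15–D28.** The documents give no operating characteristic for the rule, so there is no figure to reproduce. Each provision that could apply after day 14 was checked.

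| Provision | Applies after D14? | Group-level threshold for non-serious related events? |
|---|---|---|
| Criterion 1 | No, under the lead-in | Yes, but for 14 days only |
| Criterion 2 | Yes, by its own wording | No, related SAEs only |
| Criterion 3 | Limited by the lead-in | No, PK only |
| Principle 2, adjustment of later parts | Yes | No, discretionary |
| Principle 4 | After the maximum dose | No, general review |
| Individual withdrawal | Yes | No, subject level |
| Trial termination for unacceptable safety | Yes | No, qualitative |
| Dose Group Design, available data | Yes | No, qualitative |

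The covered share of dosing is 14/28 = 50%. Whether day 15 itself falls inside the window is immaterial.

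**Step 2: counts needed.** A group is 9 active + 3 placebo = 12 (Dose Group Design). SAP 3.5 foresees one unblinding, after database lock, so a rule applied during the trial has to be read on all 12. More than 1/2 of 12 means at least 7. More than 1/3 of 12 means at least 5.

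**Step 3: illustration for the Grade 3+ limb.** The assumptions are mine: p is the 28-day risk of a related Grade 3+ event in an active subject, the hazard is constant, and no placebo subject has an event judged related.

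- 14-day risk: q = 1 − (1 − p)^(14/28) = 1 − √(1 − p)
- 14-day counting: P(Bin(9, q) ≥ 5)
- 28-day counting: P(Bin(9, p) ≥ 5)

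For the overlap, take the fastest timetable. The 150 mg sentinels (2 active, 1 placebo) start, and the other nine subjects (7 active) start together 8 days later. The gate opens when those nine reach D14, with the sentinels at 14 + 8 = D22. The 200 mg sentinels start that day, and the other nine 200 mg subjects 8 days later. By then the 150 mg sentinels are at D30, with dosing finished, and the other 150 mg subjects are at D22. With F = 1 − (1 − p)^(22/28), the chance that the limit has been met by then is P(Bin(2, p) + Bin(7, F) ≥ 5).

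Worked case, p = 0.3: q = 1 − √0.7 = 0.163, giving 0.0082. Full counting gives 0.0988. F = 1 − 0.7^(22/28) = 0.244, giving 0.054.

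| 28-day rate p | q | 14-day counting | Cumulative, when the other nine 200 mg subjects start | 28-day counting |
|---|---|---|---|---|
| 10% | 0.051 | 0.004% | 0.04% | 0.09% |
| 20% | 0.106 | 0.1% | 1.0% | 2.0% |
| 30% | 0.163 | 0.8% | 5.4% | 9.9% |
| 40% | 0.225 | 3.2% | 16% | 27% |
| 50% | 0.293 | 9.0% | 35% | 50% |

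**Step 4: the Grade 2+ limb (at least 7).** On the same model, with p now the related Grade 2+ rate, 14-day against 28-day counting gives under 0.001% against 0.03% at 20%, and 0.07% against 2.5% at 40%.

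**Step 5: which rates are plausible.** In the synopsis safety results, drug-related events were all Grade 1 in the 25 and 50 mg multiple-dose groups and in the food-effect trial, and no single-dose event exceeded Grade 2. That points to the low end for Grade 3+. None of these data cover four weeks at 150 or 200 mg.

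**The case against.** The strongest reply is that only a prompt is missing. Meeting criterion 1 leads, under its lead-in, to a discussion between the investigator and sponsor. The same two parties already judge safety before each step, and under principle 2 "subsequent trial protocols may be appropriately adjusted based on previous safety and PK analysis results". They can also end the trial for unacceptable safety. This stands, and it keeps the point modest.

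The 14-day window also has a basis. It matches the escalation gate, and the synopsis reports near-steady-state concentrations after 14 days at 50 mg. With the longest documented single-dose mean half-life (75.1 h), day 14 is at 1 − 0.5^(24 × 14/75.1) = 95.5% of steady state. The case for change therefore rests on duration of exposure, since little further rise in concentration is expected on those half-lives. Repeat-dose behaviour at 150–200 mg is not documented.

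Finally, only one planned step is affected. An interim analysis of the 50, 75 and 100 mg groups preceded the decision to add 150 mg. The 200 mg group is an alternative that may not open, and it has its own 8-day sentinel step.

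A reader might go further in three ways that the documents do not support:

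- **That safety goes unmonitored after D14.** Adverse events are recorded to the end of the trial, and the discretionary provisions remain.
- **That related SAEs after D14 escape the rule.** Criterion 2 says it applies during the trial. Its place under a 14-day lead-in is a drafting flaw, and its specific wording should govern.
- **That the contrast is larger because 4 events among 9 active subjects suffice.** That gives 1.0% against 8.6% at a 20% rate, but a blinded group of 12 cannot be counted that way.

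**Conclusion.** The point holds in limited form. In the supplied synopsis and SAP, criterion 1 stops counting halfway through dosing, and nothing else there sets a group-level threshold for non-serious related Grade 2+ or 3+ events on D15–D28. Other protocol text was not available, so the claim extends no further.

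The gain from closing the gap is a predefined review prompt, useful mainly if 150 mg and 200 mg overlap. It is negligible if related Grade 3+ rates are near 10% and becomes material at about 30% or more. Those figures rest on assumed rates, constant hazard and no related events on placebo. The overlap column also assumes the fastest timetable. The gap in the wording depends on none of these.

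**What to change.** 1. Keep the 14-day, 50% gate in principle 2 as the earliest escalation review.
2. Remove the 14-day limit from the lead-in to the stopping criteria.
3. Begin criterion 1: *In the same dose group, counted cumulatively from the first dose through the D29 end-of-treatment assessments.* Keep the 1/2 and 1/3 thresholds and apply them, blinded, to the 12 planned subjects: at least 7 with related Grade 2+, or at least 5 with related Grade 3+.
4. State that if criterion 1 is met after a higher group has started, the investigator and sponsor hold the existing discussion and decide whether to pause or end the higher group. Reword principle 3 to match. At present it says ascending should end, while the lead-in calls for a discussion.
5. Set criterion 2 apart, so that a related SAE at any time in the trial, including follow-up to D56, suspends it.

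The cost is a short protocol amendment. Adverse-event recording, visits and reviewers are already in place, and the start of the next group is not delayed. There are two downsides: an occasional extra review while a higher group is dosing, and a somewhat stricter rule, because unchanged thresholds now run over twice the time.

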### **Pharmacodynamic Analysis**

Descriptive statistics will be used to calculate and summarize the changes from baseline in liver fat content measured by MRI-PDFF at 4 weeks and 8 weeks, the proportion of subjects with a relative reduction of at least 30% in liver fat content measured by MRI-PDFF, the changes from baseline in ALT, AST, BMI, blood lipid levels, and the changes from baseline in CAP and LSM for each group.

### **Analysis of Exploratory Indicators**

Descriptive analysis will be performed for exploratory biomarker indicators (CK18, FGF21, IP10, hsCRP, TIMP1, and  $\beta$ -HB) after administration in each dose group to explore the relationship between dose/exposure and effect of BGT-002.

The specific statistical methods are specified in the Statistical Analysis Plan.

Abbreviation Definition Adverse Events ΑE ALT Alanine Aminotransferase ANA Antinuclear antibody **AST** Aspartate aminotransferase **AUC** Area under plasma concentration-time curve Area under plasma concentration-time curve at steady state AUC_{ss} β-hydroxybutyrate β-ΗΒ Body mass index BMI CAP Controlled Attenuation Parameter CI Confidence interval CK18 Cytokeratin 18 Clearance at steady state CL_{ss}/F C_{max} Maximum plasma concentration Maximum plasma concentration at steady state $C_{\text{max, ss}}$ Minimum plasma concentration at steady state C_{min. ss} **CRF** Case report form Common Terminology Criteria for Adverse Events **CTCAE** CVCoefficient of variation **FAS** Full analysis set Fibroblast growth factor 21 FGF21 High-sensitivity C-reactive protein hsCRP IFN-γ-inducible protein 10 IP10 LSM Liver Stiffness Measurement LDL Low-density lipoprotein cholesterol Medical Dictionary for Regulatory Activities MedDRA MRI-Proton Density Fat Fraction **MRI-PDFF NASH** Non-alcoholic steatohepatitis PD Pharmacodynamics Pharmacodynamic analysis set **PDS** PK Pharmacokinetics **PKS** Pharmacokinetic set PT Preferred term Accumulation ratio R_{ac} Serious Adverse Events SAE SAP Statistical Analysis Plan SOC System Organ Class Safety Set SS Elimination half-life $t_{1/2}$ TG Triglyceride TIMP1 Tissue Inhibitor of Metalloproteinase-1 Time to maximum plasma concentration T_{max} Terminal Elimination Rate Constant λ_z

1. Introduction

This Statistical Analysis Plan (SAP) is prepared based on the clinical study protocol "A Single-center, Randomized, Double-blind, Multiple Ascending Dose, Placebo-controlled Phase Ib/IIa Clinical Trial to Evaluate the Safety, Tolerability, Pharmacokinetics and Early Pharmacodynamics of BGT-002 Tablets in Subjects with NASH" (Version No./Version Date: V2.0/2023-10-09) and CRF (Version No./Date: V2.0/2023-10-23). This SAP will fully state the methods of analysis and presentation of the data in this protocol.

2. Objectives

2.1. Primary Objective

To evaluate the safety and tolerability of BGT-002 Tablets in subjects with NASH after oral administration;

2.2. Secondary Objectives

- 1) To evaluate the pharmacokinetics (PK) of BGT-002 Tablets in subjects with NASH after oral administration;
 - 2) To evaluate the effect of BGT-002 on lipid metabolism in subjects with NASH;
- 3) To evaluate the effect of BGT-002 on biochemical indicators related to liver function in subjects with NASH.

2.3. Exploratory Objective

To evaluate the biomarker profile of BGT-002 in subjects with NASH.

3. Study Design

3.1. Overall Study Design

This study is a single-center, randomized, double-blind, multiple ascending doses (MAD), placebo-controlled phase Ib/IIa clinical trial of BGT-002 Tablets in subjects with NASH to evaluate the safety, tolerability, pharmacokinetics (PK) and early pharmacodynamics (PD) of BGT-002 Tablets.

The number of subjects: A total of 48–60 subjects are planned to be enrolled in this study.

3.2. Dose Group Design

It is originally planned to set 3-4 dose groups in this study, and the dose ascending design

is as follows: 50 mg, 75 mg, 100 mg, and 125 mg (alternative). In this trial, it is planned to start with 50 mg as the lowest dose group. During the study, whether to continue to escalate to a higher dose group or adjust the dose ascending ratio will be determined based on available data.

As of September 13, 2023, based on the results of the completed interim analysis for three dose groups (50 mg, 75 mg and 100 mg), after discussion, the Sponsor and investigator decided to add 150 mg and 200 mg (alternative) groups for a 28-day continuous administration study, with 3 sentinels in the 150 mg and 200 mg (alternative) groups, respectively (2 subjects in the test group, and 1 subject in the placebo group) and observe for 8 days. If the safety is good, the remaining subjects will continue to be enrolled in this dose group (7 subjects in the test group and 2 subjects in the placebo group).

Dose (mg)	50	75	100	150	200 (alternative)
Number of Subjects (Study Drug + Placebo)	9+3	9+3	9+3 (Male:female = close to 1:1)	9+3	9+3

Each dose group will randomly include 12 screened eligible subjects with NASH, with 9 taking the study drug orally and 3 taking the placebo orally. A total of 48-60 subjects will be included in the study. Whether to conduct the dose expansion study will be based on the results of the dose ascending phase.

Study Schedule:

	1	Hospitalization (D-1 to D8, D27 to D29)		
Screening Period (D-56~D-1)	Run-in Period (D-56~28~D-1)	Treatment and Observation Period (D1~D29)	Follow-up Period (D30~D56)	

